### 3.17 Post Treatment Follow-Up

Post-treatment follow-up (i.e., all cancer therapies including stem cell transplantation, regimens, dates of initiation and completion, etc.) will be collected at the 30-day safety follow-up visit.

### 3.18 Subject Withdrawal from Study

All attempts must be made to determine the date of the last study drug dose and the primary reason for discontinuation of study drug or study participation. The information will be recorded on the appropriate eCRF page. If a subject discontinues study participation, the procedures outlined for the Final Visit should be completed as soon as possible, preferably within 2 weeks. A 30-day safety follow-up visit will also be conducted after the last dose of study drug. If the subject refuses or is unable to attend the safety follow-up visit, this should be noted in the subject's source documentation.

However, these procedures should not interfere with the initiation of any new treatments or therapeutic modalities that the investigator feels are necessary to treat the subject's condition. Following discontinuation of study drug, the subject will be treated in accordance with the investigator's best clinical judgment, irrespective of whether or not the subject decides to continue participation in the

study. Post-treatment follow-up (i.e., all cancer therapies including stem cell transplantation, regimens, dates of initiation and completion, etc.) will be collected at the 30-day safety follow-up visit.

### 3.19 Unscheduled Visits

[figure not shown]
An Unscheduled Visit should be performed when the subject comes in for a medical visit for evaluation and assessment. During Unscheduled Visits, blood and urine samples may be obtained for the laboratory tests listed in Section 3, or for other tests, as determined by the investigator.

Visits for dispensing new study drug in case of temperature excursion, loss or damage are not considered an Unscheduled Visit. In addition, visits to only retest a lab will not be considered an Unscheduled Visit.

## 4 SAFETY MANUAL

## 4.1 Methods and Timing of Safety Assessment

All serious and nonserious adverse events which could be related to study procedures (e.g., infection at liver biopsy site, done during Screening), will be collected from the time the subject signed the study-specific informed consent until study drug administration. From the time of study drug administration until 30 days after discontinuation of study treatment, all adverse events and serious adverse events will be collected whether solicited or spontaneously reported by the subject. After 30 days following completion of study treatment and throughout the Post-Treatment Period, all spontaneously reported serious adverse events will be collected (nonserious adverse events will not be collected), except for those subjects that are able to receive commercial venetoclax treatment after the end of study participation. Any new adverse events should be reported through the mechanism used for all post marketing adverse experiences.

AE = adverse event; SAE = serious adverse event

\* Only if considered by the investigator to be causally related to study required procedures.

## 4.2 Recording Data and Analyses of Safety Findings

---

Adverse events will be coded using the Medical Dictionary for Regulatory Activities (MedDRA). The number and percentage of subjects with treatment-emergent adverse events (i.e., any event that begins or worsens in severity after initiation of study drug through 30 days post-study drug dosing) will be tabulated by primary MedDRA System Organ Class (SOC) and preferred term (PT) and compared between arms using Fisher's exact test. The tabulation of the number of subjects with treatment-emergent adverse events by severity grade and relationship to study drug also will be provided. Subjects reporting more than 1 adverse event for a given MedDRA preferred term will be counted only once for that term using the most severe grade according to the severity grade table and the most related according to the relationship to study drug tables. Subjects reporting more than 1 type of event within an SOC will be counted only once for that SOC.

## 4.3 Reporting Adverse Events and Intercurrent Illnesses

---

In the event of a serious adverse event, whether associated with study drug or not, the investigator will notify Clinical Pharmacovigilance within 24 hours of the site being made aware of the serious adverse event by entering the serious adverse event data into the electronic data capture (EDC) system. Serious adverse events that occur prior to the site having access to the RAVE® system, or if RAVE is not operable, should be documented on the serious adverse event nonCRF forms and emailed (preferred route) or faxed to Clinical Pharmacovigilance within 24 hours of the site being made aware of the serious adverse event.

Email: [[contact]](mailto:[contact])

FAX to: [contact]

For safety concerns, contact the Oncology Safety Team at:

Oncology Safety Team  
[name]  
[name]  
Office: [contact]  
Email: [SafetyManagement\\[contact]](mailto:[contact])

For any subject safety concerns, please contact the physician listed below:

#### COVID-19 Pandemic-Related Acceptable Protocol Modifications

Supplemental study case report forms should be completed in the event of COVID-19 related missed/virtual visits, study drug interruptions or discontinuations, or adverse events (including capture of specific signs/symptoms of infection and testing results).

COVID-19 infections should be captured as adverse events. If the event meets the criteria for a serious adverse event (SAE), then follow the SAE reporting directions per the protocol and above. The following COVID-19 related supplemental eCRFs should be completed (for both serious and non-serious events):

- COVID-19 Supplemental Signs/Symptoms
- COVID-19 Status Form

If a subject has a confirmed or suspected COVID-19 infection and study drug was interrupted, the investigator should contact the sponsor emergency medical contact listed above before reintroducing study drug.

## 5 COUNTRY-SPECIFIC REQUIREMENTS

### 5.1 SUSAR Reporting

---

AbbVie will be responsible for Suspected Unexpected Serious Adverse Reactions (SUSAR) reporting for the IMP in accordance with global and local guidelines and Appendix A of the Investigator Brochure will serve as the Reference Safety Information (RSI). The RSI in effect at the start of a DSUR reporting period serves as the RSI during the reporting period. For follow-up reports, the RSI in place at the time of occurrence of the 'suspected' Serious Adverse Reaction will be used to assess expectedness.

## 6 STUDY DRUG

### 6.1 Treatments Administered

---

Venetoclax will be dispensed in the form of 10-, 50-, and 100-mg film-coated tablets at the visits listed in Section 2.1 (refer to the Protocol Section 5.7). Each dose of venetoclax will be taken with approximately 240 mL of water. Subjects will be trained to self-administer venetoclax orally once daily (QD) **within 30 minutes after the completion of breakfast or the subject's first meal of the day**. On the days the subject is given either azacitidine or decitabine, venetoclax must be dosed in clinic and administered prior to these agents.

Venetoclax tablets should be swallowed whole and not chewed, crushed, or broken prior to swallowing. If a subject should forget to take his/her venetoclax dose at his/her regularly scheduled dosing time, the subject should take the forgotten dose as soon as he/she remembers, provided that the dose will be taken within 8 hours of the missed dose. Otherwise, the subject should take the next dose at the next scheduled dosing time. If the subject vomits within 15 minutes of taking venetoclax, no additional dose should be taken that day. The next prescribed dose should be taken at the usual time.

Depending on the investigator's choice, subjects will receive azacitidine or decitabine on Cycle 1 Day 1. The subject is to remain on their assigned therapy for the duration of this study. Azacitidine (75 mg/m^2) infusions or injection and decitabine (20 mg/m^2) infusions should be prepared and administered per the respective package inserts. Azacitidine will be administered subcutaneously or intravenously beginning on Day 1 for 7 days of each 28-day cycle, as per institutional practice. Decitabine will be administered intravenously beginning on Day 1 for 5 days of each 28-day cycle, as per institutional practice.

AbbVie will provide venetoclax. AbbVie provided study drug should not be substituted or alternately sourced unless otherwise directed by AbbVie.

Study drug must not be dispensed without contacting the Interactive Response Technology (IRT) system. Study drug may only be dispensed to subjects enrolled in the study through the IRT system. At the end of the Treatment Period or at the final visit (Cycle 6 Day 28), the site will contact the IRT system to provide visit date information and study drug return information for each kit.

## 6.2 Packaging and Labeling

---

The venetoclax tablets will be packaged in high density polyethylene (HDPE) plastic bottles or blister cards to accommodate the study design. Each bottle or blister card will be labeled per local regulatory requirements. The labels must remain affixed to the bottles. All blank spaces should be completed by site staff prior to dispensing to subject.

The site will be responsible for obtaining azacitidine or decitabine.

### Storage and Disposition of Study Drug

Venetoclax must be stored at controlled room temperature (15° to 25°C /59° to 77°F).

The investigational products are for investigational use only and are to be used only within the context of this study. The study drug supplied for this study must be maintained under adequate security and stored under the conditions specified on the label until dispensed for subject use, destroyed on site, or returned to AbbVie, as appropriate.

## 6.3 Method of Assigning Subjects to Treatment Groups

---

This is a non-randomized, open-label study. All eligible subjects will receive venetoclax QD in combination with azacitidine or decitabine as described in Section 2.1. The choice of azacitidine or decitabine will be as determined by the investigator. The subject is to remain on their assigned therapy for the duration of the study.

At the Screening visit, all subjects will be assigned a unique subject number through the use of the IRT. For subjects who do not meet the study selection criteria, the site personnel must contact the IRT system and identify the subject as a screen failure.

Subjects who are enrolled will retain their subject number assigned at the Screening visit throughout the study. Upon receipt of study drug, the site will acknowledge receipt in the IRT system.

Contact information and user guidelines for IRT use will be provided to each site.

## 6.4 Selection and Timing of Dose for Each Subject

---

Selection of the doses for this study is discussed in the study protocol, Section 4.2.

All tablets of venetoclax will be dosed together, QD for 28-day cycles. Azacitidine will be administered either SC or intravenously (IV), and decitabine will be administered IV. All subjects should take all doses of study drug with food around the same time each day, as described in Section 6.1. On the days the subject is given either azacitidine or decitabine, venetoclax must be dosed in clinic and administered prior to these agents.

All subjects will be treated with venetoclax and azacitidine or decitabine for a maximum of six cycles (28 days each). Subjects will undergo a final visit when treatment is discontinued or at the end of the sixth cycle. After the study period ends, subjects may continue receiving AML-directed therapy

including commercially-acquired standard-of-care treatments for venetoclax and azacitidine or decitabine.

3.0 Introduction

The statistical analysis plan describes the analyses of safety and efficacy data collected for Study M19-072. Analysis conventions to guide statistical programming conventions are provided.

Analyses will be performed using SAS Version 9.4 or higher.

4.0 Study Background

4.1 Objectives

Primary:

- To determine the composite complete remission rate (CR + CRi), during the initial 6 cycles of treatment, as determined by the modified International Working Group (IWG) criteria, of venetoclax in combination with azacitidine or decitabine given in an outpatient setting to treatment-naïve subjects with AML who are ineligible for intensive chemotherapy.

Secondary:

- To determine the incidence and severity of adverse events including, but not limited to, rates of TLS and neutropenia
- To assess the rate of transfusion independence upon treatment with venetoclax and azacitidine or decitabine.

4.2 Study Design

The study is a Phase 3b, open-label, single-arm, multicenter study evaluating the composite complete remission rate and safety of venetoclax in combination with azacitidine or decitabine in an outpatient setting for treatment-naïve subjects with AML who are ineligible for intensive chemotherapy.

Approximately 60 subjects will be enrolled in the trial. Treatment will be initiated with a venetoclax dose ramp-up over three days and adjusted as appropriate with concomitant use of CYP3A inhibitors. Ramp-up activities for subjects in this study will be done in an outpatient setting. The choice of azacitidine or decitabine will be made at the discretion of the investigator: the subject is to remain on their assigned therapy for the duration of the study.

All subjects will receive venetoclax daily. Subjects will receive either azacitidine for seven days or decitabine for five days of each 28 day cycle up to 6 cycles. After the sixth cycle, subjects may continue to receive AML-directed therapy, including commercially acquired venetoclax with azacitidine or decitabine, outside of this study protocol.

Subjects with progressive disease for whom the treating physician feels are still deriving clinical benefit can be continued on treatment until no longer achieving clinical benefit, unacceptable toxicity, withdrawal of consent, or other protocol criteria for discontinuation are met. All subjects will have a final visit performed when treatment is discontinued and a 30-day safety follow-up assessment.

4.3 Endpoints

4.3.1 Primary Efficacy Endpoint

The primary endpoint is the composite complete remission rate (CR + CRi): complete remission (CR) plus complete remission with incomplete hematologic recovery (CRi) as described by the modified IWG criteria (Operations Manual, Section 3.15).

4.3.2 Secondary Efficacy Endpoints

The secondary endpoints are:

- Response of CR or CRi: complete remission (CR) or complete remission with incomplete hematologic recovery (CRi) as described by the modified IWG criteria.

- Transfusion independence rate is defined as the proportion of subjects who achieved post-baseline transfusion independence, which is defined as a period of at least 56 days with no transfusion after the first dose of study drug and within 30 days of the last dose of study drug, death, initiation of post-treatment therapy, whichever is earliest. Transfusion independence rate will be calculated for both RBC transfusion and platelet transfusion separately and together.

4.3.3 Exploratory Efficacy Endpoints

The exploratory endpoints are:

- Time to the first improvement of absolute neutrophil count (ANC), platelets, and hemoglobin as well as duration of the first improvement of absolute neutrophil count, platelets and hemoglobin. See Section 9.4.1 for definitions of both endpoints.
- Rates of CR/CRI in molecular subtypes identified per institutional practices.

4.3.4 Safety Endpoint

Safety evaluations will include adverse event monitoring, clinical lab testing, vital signs measurements, and rate of hospitalization.

4.4 Sample Size Justification

A sample size of 60 subjects would ensure that the true CR + CRI rate will be within 13% of the observed rate with 95% confidence.

4.5 Interim Analysis

None are planned.

5.0 Analysis Populations

5.1 Definition of Analysis Populations

Subjects who receive at least one dose of venetoclax, azacitidine, or decitabine will be included in all analyses unless specified otherwise.

5.2 Definition of Treatment Groups

Subjects will receive venetoclax in combination with one hypomethylating agent, either azacitidine or decitabine. Study results will be presented for 3 groups: Venetoclax in combination with either azacitidine or decitabine and for all treated subjects combined.

6.0 Analysis Conventions

6.1 Definition of Study Drug

Study drug in this document refers to venetoclax and hypomethylating agents azacitidine and decitabine.

6.2 Definition of Baseline

Baseline for a given variable will be the last value obtained on or prior to the first dose of any component of study drug.

6.3 Definition of Final Observation

The final observation is defined as the last non-missing observation collected after the first dose of any component of study drug to the last dose of any component of study drug + 30 days.

6.4 Definition of Rx Days

Study Day is defined as the number of days since or prior to the first dose of any component of study drugs. The day of the first dose of study drug is defined as study Day 1, while the day prior to the first dose of study drug is study Day –1.

7.0 Demographics, Baseline Characteristics, Medical History, Prior and Post-treatment Systemic Therapies, and Concomitant Medications

All analysis in this session will be summarized for the 3 treatment groups: venetoclax in combination with either azacitidine or decitabine, and all treated subjects combined. The number of subjects with missing information will also be summarized. There will be no statistical comparison for the variables summarized in this section.

7.1 Demographic and Baseline Characteristics

All baseline characteristic summary statistics and analyses are based on characteristics prior to the first dose of study drug.

Summaries of continuous characteristics will consist of the number of non-missing observations, mean, standard deviation, and range. Categorical characteristics will be summarized by the frequencies and percentages of subjects within each category.

The following demographic, baseline, and disease-related characteristics will be summarized:

Demographics:

Age (years) and age categories (12 – < 18, 18 – < 65, 65 – < 75 years, ≥ 75 years)

Gender (male, female)

Race (White, Black or African American, Asian, American Indian or Alaska Native, Native Hawaiian or Other Pacific Islander)

Ethnicity (Hispanic or Latino vs. Not Hispanic or Latino)

Height (cm)

Weight (kg)

Baseline and Disease-Related Characteristics:

ECOG performance status (Grade 0, 1, 2, 3)

Cytogenetic risk (favorable, intermediate, poor)

Bone marrow blast count (< 30%, ≥ 30% – < 50%, ≥ 50%)

Bone marrow blast count (%)

White blood cell count ($\times 10^9/\text{L}$)

CTC grade of neutropenia

Neutrophil value ($\times 10^9/\text{L}$)

CTC grade of anemia

Hemoglobin value (G/L)

CTC grade of thrombocytopenia

Platelet count ($\times 10^9/\text{L}$)

Type of AML (de novo, secondary, therapy-related AML)

Reasons for being ineligible for standard induction therapy

Antecedent hematologic history of MDS or MPN (Yes, No)

Baseline packed RBC transfusion dependence (Yes, No)

Baseline platelet transfusion dependence (Yes, No)

Molecular marker (FLT3-ITD, FLT3-TKD, IDH1, IDH2, IDH1/2, TP53, NPM1, CEBPA, TET2, ASXL1, DNMT3A, Other)

Hepatic impairment (Yes [Mild Impairment, Moderate Impairment, Severe Impairment], No)

Renal impairment (Yes [Mild Impairment, Moderate Impairment, Severe Impairment], No)

7.2 Medical History

Medical history will be summarized according to the MedDRA dictionary, with presentation organized by system organ class (SOC) and preferred term (PT). The SOCs will be presented in alphabetical order and the PTs will be presented in alphabetical order within each body system. The number and percentage of subject with a particular PT will be summarized. Subjects reporting more than one PT within a SOC will be counted only once for that SOC.

7.3 Prior and Post-treatment Systemic Therapies and Concomitant Medications

A prior medication is defined as any medication taken prior to the first dose of study drug. A concomitant medication is defined as any medication that started prior to the first dose of study drug and continued to be taken after the first dose of study drug, or any medication that started after the first dose of study drug, but not after the last dose of study drug.

The number and percentage of subjects who took at least one dose of concomitant medication other than study drug will be summarized by the generic medication name coded by WHO dictionary. A subject who reports the use of two or more medications with same start date will be counted only once in the summary of "Any Concomitant Medication." A subject who reports two or more uses of the same medication will be counted only once in the total for the associated WHO generic drug name.

The number and percentage of subjects who have prior or post-treatment systemic therapies will be summarized by generic medication name coded by WHO dictionary.

The number and percentage of subjects who have taken TLS prophylaxis agents including intravenous hydration on or prior to the first dose of study drug and concomitant to the study treatment will be summarized separately.

The number and percentage of subjects who have received transfusions on or prior to first dose of study drug will be summarized by transfusion type.

8.0 Patient Disposition and Study Drug Exposure

All analysis in this session will be summarized for the 3 treatment groups: venetoclax in combination with either azacitidine or decitabine, and all treated subjects combined. The number of subjects with missing information will also be summarized. There will be no statistical comparison for the variables summarized in this session.

8.1 Patient Disposition

The number of screen failures and screen failure reasons will be tabulated. The numbers and percentages of subjects will be summarized by treatment groups for each of the following categories for all enrolled subjects:

- Subjects enrolled into the study
- Subjects who received at least one dose of study drug
- Subjects who were enrolled but not treated with any component of study drug
- Subjects who discontinued venetoclax due to all reasons and primary reason
- Subjects who discontinued azacitidine due to all reasons and primary reason
- Subjects who discontinued decitabine due to all reasons and primary reason

8.2 Study Drug Exposure

Exposure to each of the three study drugs will be summarized in days using sample size (N), mean, standard deviation, median, and range for each of the following variable:

- The duration of exposure which is defined for each subject as (last dose date – first dose date) + 1;

- The number of cycles that subjects were exposed to study drug.
- Average dosed days per cycle which is defined for each subject as (total number of days subject received study drug)/(the number of cycles subject was exposed to study drug).
- Dose intensity accounting for dose reduction.
- Dose intensity accounting for dose reduction and interruption.

The number and percentage of subjects with dose reduction or dose interruption will be summarized by the number of occurrences of dose reduction or interruption as no, 1 time, 2 times, or > 2 times.

In addition, the number and percentage of subjects exposed to each of the three study drugs will be summarized for the following categories of exposure duration:

- 0 to 4 weeks (0 to 28 days),
- 4 weeks to 8 weeks (28 to 56 days),
- 8 weeks to 12 weeks (57 to 84 days),
- 12 weeks to 16 weeks (85 to 112 days),
- 16 weeks to 20 weeks (113 to 140 days),
- 20 weeks to 24 weeks (141 to 168 days).

The number and percentage of subjects who received CYP3A inhibitors and/or P-gp inhibitors during the period from first exposure to study drug to last exposure of study drug will be summarized by the type: moderate/strong CYP3A inhibitor, moderate P-gp inhibitors.

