### [Management of Cytopenias](#)

Myelosuppression and the related adverse events (thrombocytopenia, anemia, neutropenia, and febrile neutropenia) are common in both treated and untreated patients with AML. Subjects with baseline neutropenia or those who have significant bone marrow involvement may be particularly at high risk.

If a subject achieves CRi or has a morphologic leukemia free bone marrow (MLFS) (i.e., bone marrow blasts  $< 5\%$ ) after completion of Cycle 1, venetoclax should be interrupted to allow for ANC recovery from Day 29 until  $\text{ANC} \geq 500/\mu\text{L}$  or up to 14 days.

Cycle 2 administration of azacitidine or decitabine will also be delayed until  $\text{ANC} \geq 500/\mu\text{L}$ . Both venetoclax and azacitidine or decitabine will resume on the same day after the interruption. If a subject presents with new onset Grade 4 neutropenia for more than 1 week during subsequent cycles, unless it is thought to be due to the underlying disease, dosing with venetoclax and azacitidine or decitabine may be interrupted until  $\text{ANC} \geq 500/\mu\text{L}$ .

After Cycle 3, for subjects in CR/CRi who required interruption or delay of study drug administration for cytopenias (neutropenia [ $\leq 500/\mu\text{L}$ ] or thrombocytopenia [ $\leq 50 \times 10^3/\mu\text{L}$ ]) venetoclax should be administered for 21 days out of 28 days during each of the subsequent cycles. The treatment cycle should also be delayed to allow for count recovery until  $\text{ANC} \geq 500/\mu\text{L}$ , platelet count  $\geq 50 \times 10^3/\mu\text{L}$ , or for up to 14 days, whichever occurs earlier.

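### SAP 8.2's exposure-duration categories count Day 28 twice and have no row above 168 days, so venetoclax taken through Cycle 6 Day 28 after any cycle delay is unclassified

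*SAP*

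**What the plan says.** SAP 8.2 (Study Drug Exposure) defines the variable as follows: "The duration of exposure which is defined for each subject as (last dose date – first dose date) + 1". Days without dosing between the first and last dose are not subtracted. The categorical display is per drug: "the number and percentage of subjects exposed to each of the three study drugs will be summarized for the following categories of exposure duration".

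The first three rows read "0 to 4 weeks (0 to 28 days", "4 weeks to 8 weeks (28 to 56 days" and "8 weeks to 12 weeks (57 to 84 days". The series continues in 28-day steps to "20 weeks to 24 weeks (141 to 168 days", which is the final row.

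On treatment length, section 6.4 of the Operations Manual (Protocol Appendix J) has subjects treated "for a maximum of six cycles (28 days each". Protocol 5.7 runs venetoclax from Cycle 1 Day 1 to Cycle 6 Day 28, with azacitidine for 7 days and decitabine for 5 days from Day 1 of each cycle.

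The protocol also provides for delay:

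- Section 6.2 (Management of Cytopenias): for subjects in CRi or MLFS after Cycle 1, "venetoclax should be interrupted to allow for ANC recovery from Day 29 until" the neutrophil count recovers, or for up to 14 days.
- Same section: after Cycle 3, subjects in CR/CRi who needed an interruption or delay for cytopenias take venetoclax on 21 of 28 days. Cycles may again be held for up to 14 days for count recovery.
- Section 6.1 (Adverse Events of Special Interest): an unrelated medical event may delay treatment by up to 4 weeks.

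**The concern.** A frequency table needs each subject to fall in exactly one row. Here the first two rows share an endpoint, and the last row closes at the length of six cycles with no delay, although delay is part of the planned regimen and counts towards the duration.

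Day 28 is a plausible value, not a curiosity: a subject who takes venetoclax through Cycle 1 Day 28 and then stops has a duration of exactly 28 days. At the other end, the subjects without a row have completed all six cycles and been delayed on the way. The count-recovery delays are tied to marrow response, whereas subjects with resistant disease continue without delay. The unclassified subjects would therefore tend to include responders, although delays for unrelated events can affect anyone. Programmed as written, the row percentages need not add to 100%, and the table can disagree with the maximum duration reported beside it.

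**Working it through.** **Reproducing the plan's upper bound.** 6 cycles × 28 days = 168 days. This matches the last row, but it is the length without delay, not a maximum.

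**Row boundaries.** Checking every whole-day duration from 0 to 259 against the six printed rows:

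- the only duration in two rows is 28 days;
- there is no gap between 0 and 168 days;
- the first duration in no row is 169 days.

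**Duration for a subject who completes six cycles.** Let L be the last dosing day in Cycle 6 and T the total number of days by which delays push back the start of Cycle 6. Then

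duration = 5 × 28 + L + T = 140 + L + T.

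The subject stays in the last row while 140 + L + T ≤ 168, that is, while T ≤ 28 − L.

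| Drug and Cycle 6 schedule | L | Duration, T = 0 | Largest T with a row | Duration, T = 14 | Duration, T = 28 |
|---|---|---|---|---|---|
| Venetoclax, Days 1–28 | 28 | 168 | 0 | 182 (no row) | 196 (no row) |
| Venetoclax, 21 of 28 days, taken as Days 1–21 | 21 | 161 | 7 | 175 (no row) | 189 (no row) |
| Azacitidine, Days 1–7 | 7 | 147 | 21 | 161 (has a row) | 175 (no row) |
| Decitabine, Days 1–5 | 5 | 145 | 23 | 159 (has a row) | 173 (no row) |

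L = 28, 7 and 5 follow from Protocol 5.7 if the azacitidine and decitabine days are consecutive. L = 21 assumes that the 21 dosing days come first in the cycle; the protocol does not say which days they are. T = 14 is one full count-recovery delay and T = 28 is one full delay for an unrelated event.

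**Check of the repair.** With the second row at 29–56 days and an added row above 168 days, every whole-day duration from 0 upward falls in exactly one row.

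**The case against.** The strongest reply is that little depends on this table. SAP 8.2 also summarises the same duration by N, mean, SD, median and range without a cap. It reports cycles, dosed days per cycle, dose intensity, and reductions and interruptions as well. Long exposures therefore stay visible, and that stands: a reader might infer that the reported exposure distribution as a whole is truncated, and it is not.

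The shared 28 also looks like a typing slip, since every later row starts one day after the previous row ends. That is fair, but a slip at one boundary does not explain the missing top row, and the SAP says that its conventions are there to guide programming. Nor does the count of subjects with missing information (SAP 8.0) cover these subjects, because their durations are known.

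Three stronger readings are tempting and go too far:

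- **That every delayed six-cycle completer loses a row.** The rows apply to each drug separately. A single 14-day delay leaves azacitidine and decitabine in the last row, and venetoclax on Days 1–21 of Cycle 6 tolerates up to 7 days.
- **That venetoclax durations in delayed remitters reach 238 days (168 + 5 × 14).** This ignores the move to 21 of 28 days for subjects in CR/CRi who needed such delays. With Days 1–21 in Cycle 6, the figure is 140 + 21 + 70 = 231.
- **That some definite share of the population is lost.** The documents give neither a six-cycle completion rate nor a delay rate, so the affected proportion cannot be estimated from them.

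**Conclusion.** Wrong as written, with minor consequences. The categories double-count a duration of 28 days and omit every duration of 169 days or more. A subject dosed with venetoclax through Cycle 6 Day 28 is unclassified after as little as one day of total delay. On the 21-of-28-day schedule this starts at 8 days of total delay, for azacitidine at 22 and for decitabine at 24.

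These thresholds assume venetoclax on Days 1–21 under the shortened schedule and consecutive azacitidine or decitabine dosing from Day 1. Because dosing follows institutional practice, each day by which a non-consecutive schedule moves the last dose later shortens the margin by one day. The defect itself does not depend on these assumptions; only the thresholds do.

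The effect stops at this descriptive frequency table. No efficacy result and no sample-size figure depends on it.

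**What to change.** In SAP 8.2, change the second row to 29 to 56 days and add a final row for more than 168 days. The rows then read 0–28, 29–56, 57–84, 85–112, 113–140, 141–168 and >168 days.

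Leave the first row starting at 0. SAP 5.1 admits subjects who received any one of the three drugs, so a treated subject can have zero days of a particular drug. Starting at 1 would leave that subject without a row if all treated subjects form the denominator.

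The cost is an edit to the SAP text and the table shell. Data collection, the definition of duration and the other exposure summaries stay as they are.
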